### 9.9. Appendix I Schedule of Assessments (Part 2 For Participants Who Receive The Booster Dose)

Visit Number	0	1	2	3	4	5	6	7	8	9	10	-	11	-	12			
Type of Visit	C	C	C	C	Virtu al Call	C	C	C	C	Virtu al Call	C	Virtual Call	SFU	C	SFU	C		
Month Point	M0		M1			M2		M5					eDiar y	SC	M11	eDiar y	SC	M17
Study Visit Day																		
Window Allowance (Days)	-7		+3	+7	-2	+3	+7	-28	-2	+3	+7	±3	±3	+7	±3	±3	±3	
Days Since Most Recent Injection	-	0	7	28	3	7	28	120	3	7	28	-	-	180	-	-	365	
Informed consent/assent form, demographics, concomitant medications, medical history																		
Review of inclusion and exclusion criteria			X	X														

Visit Number	0	1	2	3	4	5	6	7	8	9	10	-	11	-	12
Type of Visit	C	C	C	C	Virtu al Call	C	C	C	C	Virtu al Call	C	SFU	C	SFU	C
Month Point	M0		M1		M2	M5				eDiar y	SC	M11	eDiar y	SC	M17
Study Visit Day															
Window Allowance (Days)	-7		+3	+7	-2	+3	+7	-28	-2	+3	+7	±3	±3	±3	±4
Days Since Most Recent Injection	-	0	7	28	3	7	28	120	3	7	28	-	-	180	-
Physical examination including vital signs, height, weight 														X	
Pregnancy test 	X	X										X			
Study injection (including 30-minute post-dose observation period)												X			
Blood sample for potential biomarker analysis 												X			

Visit Number	0	1	2	3	4	5	6	7	8	9	10	-	11	-	12	
Type of Visit	C	C	C	C	Virtu al Call	C	C	C	C	Virtu al Call	C	SFU	C	SFU	C	
Month Point		M0		M1		M2	M5					eDiar y	M11	eDiar y	SC	M17
Study Visit Day																
Window Allowance (Days)	-7		+3	+7	-2	+3	+7	-28	-2	+3	+7	±3	±3	±3	±3	±14
Days Since Most Recent Injection	-	0	7	28	3	7	28	120	3	7	28	-	-	180	-	-365
Blood sample for immunogenicity 												X		X		X
Nasal swab for SARS-CoV-2 												X		X		
Surveillance for COVID-19/ Illness visit  / Unscheduled visit												X	X	X	X	X
Convalescent Visit 												X	X	X	X	X

Visit Number	0	1	2	3	4	5	6	7	8	9	10	-	11	-	12		
Type of Visit	C	C	C	C	Virtu al Call	C	C	C	Virtu al Call	C	Virtu al Call	C	SFU	C	SFU		
Month Point	M0		M1		M2		M5						eDiar y	M11	eDiar y	SC	M17
Study Visit Day																	
Window Allowance (Days)	-7		+3	+7	-2	+3	+7	-28	-2	+3	+7	±3	±3	+7	±3	±3	±14
Days Since Most Recent Injection	-	0	7	28	3	7	28	120	3	7	28	-	-	180	-	-	365
eDiary activation for recording solicited ARs (7 days) 										X			X				
Review of eDiary data										X			X				
Follow-up safety telephone calls 													X		X		

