Note: All scheduled study visits should be completed within the respective visit windows. If the participant is not able to attend a study site visit as a result of the COVID 19 pandemic (self-quarantine or disruption of study site activities following business continuity plans and/or local government mandates for “stay at home” or “shelter in place”), a safety telephone call to the participant should be made in place of the study site visit. The safety telephone call should encompass all scheduled visit assessments that can be completed remotely, such as assessment for AEs and concomitant medications (eg, as defined in scheduled safety telephone calls). Home visits will be permitted for all nondosing visits, with the exception of Screening, if a participant cannot visit the study site as a result of the COVID-19 pandemic. Home visits must be permitted by the study site IRB and the participant via informed consent/assent and have prior approval from the Sponsor (or its designee).

1. Day 0 and Day 1 may be combined on the same day. Additionally, the Day 0 visit may be performed over multiple visits if preformed within the 7-day screening window. If eligible, participants will receive 50 µg mRNA-1273 28 days apart and will receive a BD at least 3 months from second dose.
2. If the visit for the second dose (Day 29) or BD (Day 149) is disrupted and cannot be completed at Day 29 +7 or at Day 149 -28 days as a result of the COVID-19 pandemic (self-quarantine or disruption of study site activities following business continuity plans and/or local government mandates for “stay at home” or “shelter in place”), the visit window may be extended to Day 29 + 21 days or Day 149 +21 days. When the extended visit window is used, the remaining study visits should be rescheduled to follow the inter-visit interval from the actual date of the second dose.
  1. Safety follow-up via an eDiary questionnaire will be performed every 4 weeks from Day 191 to Day 303 and again from Day 343 to Day 455.
  2. Safety follow-up via a safety telephone call will be performed every 4 weeks from Day 205 to Day 317 and again from Day 357 to Day 469.

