2. If the visit for the second dose (Day 29) is disrupted and cannot be completed at Day 29 +7 due to the COVID-19 pandemic (self-quarantine or disruption of study site activities following business continuity plans and/or local government mandates for “stay at home” or “shelter in place”), the visit window may be extended to Day 29 + 21 days. When the extended visit window is used, the remaining study visits should be rescheduled to follow the inter-visit interval from the actual date of the second dose.
3. Safety follow-up via an eDiary questionnaire will be performed every 4 weeks from Day 99 to Day 183 and again from Day 223 to Day 307.
4. Safety follow-up via a safety telephone call will be performed every 4 weeks from Day 113 to Day 197 and again from Day 237 to Day 321.
5. Review of inclusion and exclusion criteria will be conducted during Screening. However, this review may be conducted on Day 1 if Screening and Baseline procedures are conducted on the same day.
6. Physical examination: A full physical examination, including height, weight, and vital signs will be performed at Screening, Day 1, Day 29, Day 57, Day 209, and Day 394. BMI will be calculated only at Screening Visit (Day 0). Symptom-directed physical examinations may be performed at other timepoints at the discretion of the investigator. On each injection day before injection and again 7 days after injection, the arm receiving the injection should be examined and the associated lymph nodes should be evaluated. Any clinically significant finding identified during a study visit should be reported as a MAAE. Vital signs are to be measured predose and postdose on days of injection (Day 1 and Day 29). When applicable, vital signs should be measured before blood collection. Participants who are febrile (body temperature  $\geq 38.0^{\circ}\text{C}/100.4^{\circ}\text{F}$ ) before injection on Day 1 and Day 29 must have the visit rescheduled within the relevant visit window to receive the injection. Afebrile participants with minor illnesses can be enrolled at the discretion of the investigator.
7. Pregnancy test at Screening and Day 1, and before the second study injection will be a point-of-care urine test. At the discretion of the investigator, a pregnancy test either via blood or point-of-care urine test can be performed at any time.
8. Serum sample from two ~4 mL blood draws. Biomarker plasma and biomarker serum samples will be stored for potential future biomarker assessment.

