#### Baseline SARS-CoV-2 Status for Each Part

- **Pre-Dose 1 SARS-CoV-2 status for long-term analysis** is determined by using virologic and serologic evidence of SARS-CoV-2 infection on or before the date of first dose of mRNA-1273 (the first dose of mRNA-1273 in Part 1A for subject who receive mRNA-1273 in Part 1A or the first dose of mRNA-1273 in Part 1B for subjects who receive Placebo in Part 1A).

Negative SARS-CoV-2 status for long-term analysis is defined as a most recent negative RT-PCR test for SARS-CoV-2 and a most recent negative serology test based on bAb specific to SARS-CoV-2 nucleocapsid (as measured by *Roche Elecsys Anti-SARS-CoV-2 assay*) on or before the date of the first dose of mRNA-1273.

Positive SARS-CoV-2 status for long-term analysis is defined as a most recent positive RT-PCR test for SARS-CoV-2 at the date of the first mRNA-1273 dose, and/or a most recent positive serology test based on bAb specific to SARS-CoV-2

nucleocapsid (as measured by *Roche Elecsys Anti-SARS-CoV-2 assay*) on or before the date of the first dose of mRNA-1273.

- **Pre-booster SARS-CoV-2 Status**

**Pre-booster SARS-CoV-2 status** for Part 1C-1 and Part 1C-2 is determined by using virologic and serologic evidence of SARS-CoV-2 infection on or before the date of booster dose (BD-Day 1).

Pre-booster positive SARS-CoV-2 status is defined as a positive RT-PCR test for SARS-CoV-2, and/or a positive serology test based on bAb specific to SARS-CoV-2 nucleocapsid (as measured by *Roche Elecsys Anti-SARS-CoV-2 assay*) on or before BD-Day 1.

Pre-booster negative status is defined as a negative RT-PCR test for SARS-CoV-2 and a negative serology test based on bAb specific to SARS-CoV-2 nucleocapsid (as measured by *Roche Elecsys Anti-SARS-CoV-2 assay*) on or before BD-Day 1.

- **Baseline SARS-CoV-2 status for Part 2 and Part 3** is defined using the same approach as Part 1A.

**Study day relative to the first** injection in Part 1B or Part 2 or Part 3 will be calculated as below:

- a) study day prior to the first injection will be calculated as: date of assessment/event – date of the first injection in Part 1B or Part 2 or Part 3;
- b) study day on or after the date of the first injection will be calculated as: date of assessment/event – date of the first injection in Part 1B or Part 2 or Part 3 + 1;

**Study day relative to the booster** injection in Part 1C-1 or Part 1C-2 or Part 2 (for participants who receive booster dose) will be calculated as below:

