### 8.2. Appendix B Analysis Visit Windows for Safety and Immunogenicity Analysis

Safety and Immunogenicity Analysis will be summarized using the following analysis visit window for post injection assessments:

Step 1: If the safety and immunogenicity assessments are collected at scheduled visit, i.e. nominal scheduled visit, the data collected at scheduled visit will be used.

Step 2: If the safety and immunogenicity assessments are not collected at the scheduled visit, assessments collected at unscheduled visit will be used using the analysis visit windows described in Table 3 below.

If a subject has multiple assessments within the same analysis visit, the following rule will be used:

- If multiple assessments occur within a given analysis visit, the assessment closest to the target study day will be used.
- If there are 2 or more assessments equal distance to the target study day, the last assessment will be used.

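### Table 3 counts the Part 2 booster antibody windows from dose 1, so an unscheduled replacement sample can be filed on the wrong side of the booster; Appendix I footnote 2 has a related timing slip.

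*SAP*

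**What the plan says.** **Labelling rule.** Section 8.2, Appendix B of the SAP for Parts 1B, 1C, 2 and 3 works in two steps. Step 1 covers samples drawn at a scheduled visit: "nominal scheduled visit, the data collected at scheduled visit will be used". Step 2 is the fallback: "If the safety and immunogenicity assessments are not collected at the scheduled visit, assessments collected at unscheduled visit will be used", placed by the Table 3 windows.

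**Windows.** For Part 2 participants who receive the booster, the immunogenicity rows of Table 3 are Day 149 [104, 163], Day 177 [164, 253], Day 329 [254, 422] and Day 514 (423 or later), all counted from the first injection. The Part 1C rows of the same table are counted from the booster day. Section 6.1 also defines a booster-relative study day that covers Part 2: "injection in Part 1C-1 or Part 1C-2 or Part 2 (for participants who receive booster dose) will be calculated as below".

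**Visit schedule.** Appendix I (Section 9.9 of the SAP for Part 1A) places the later visits 3, 7, 28, 180 and 365 days after the booster, in its row "Days Since Most Recent Injection". Footnote 2 says that, after pandemic disruption, "the visit window may be extended to Day 29 + 21 days or Day 149 +21 days", and that "the remaining study visits should be rescheduled to follow the inter-visit interval from the actual date of the second dose". Appendix J, the two-dose Part 2 schedule, carries the same re-timing sentence after extending dose 2 alone.

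**The concern.** The Part 2 booster day can move. The ordinary allowance at Day 149 is -28 days (Day 121 to 149), and the extension runs to Day 170. A window fixed to dose 1 does not move with it. Because no row carries a before-booster or after-booster condition, a Step 2 sample can land on the wrong side of the injection. A boosted titer would then raise the pre-booster geometric mean, or an unboosted titer would lower the Day 177 mean.

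The footnote is a second, separate slip. In Appendix J the second dose is the last dose, so it is the right anchor. In Appendix I the booster may be the delayed dose, yet the anchor named is still dose 2. Taken at its word, the sentence contradicts the schedule's own intervals.

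**Working it through.** **Inputs.** Booster day b: 121 to 149 (ordinary) or 150 to 170 (extended), from Appendix I. Planned intervals after the booster: 3, 28, 180 and 365 days. Allowance at the 28-day visit: +7. Windows from Table 3.

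**Reproducing the plan's days and windows.**
- Visits: 149 + 28 = 177; 149 + 180 = 329; 149 + 365 = 514; latest booster 149 + 21 = 170.
- Cut points are midpoints of fixed dose-1 days: (57 + 149)/2 = 103; (149 + 177)/2 = 163; (177 + 329)/2 = 253; (329 + 514)/2 = 421.5. These match Table 3, so the rows are indeed counted from dose 1.

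**Wrong label, Step 2 only.**
- Booster on Day 149, scheduled Day 149 sample missing: an unscheduled sample on Day 150 to 163 is 1 to 14 days post-booster (163 - 149 = 14) and lies in [104, 163], so it is labelled Day 149.
- Early booster, scheduled Day 149 sample missing: an unscheduled sample 28 days after the booster is labelled Day 149 when b + 28 ≤ 163, that is b ≤ 135. This holds for b = 121 to 135, 15 of the 29 ordinary days.
- Late booster, scheduled Day 177 sample missing: an unscheduled pre-booster sample on Day 164 to b - 1 lies in [164, 253] and is labelled Day 177. Such a day exists when b - 1 ≥ 164, so for b = 165 to 170, 6 of the 21 extended days. A pre-dose sample on the booster day itself is the scheduled one and keeps its label.

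**Wrong timing under a correct label: footnote read literally, dose 2 on Day 29.**
- Day 177 sample: 177 - b = 27 down to 7 days post-booster for b = 150 to 170.
- At the +7 limit: 184 - b = 34 down to 14. It reaches 28 for b ≤ 156 (7 of 21 days) and cannot for b = 157 to 170 (14 of 21 days).
- The 3-day visit (149 + 3 = Day 152) would come before the booster for b = 153 to 170 (18 of 21 days).

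**Limits for re-anchored rows** (booster-relative day = study day - 149 + 1). 253 becomes 105, 254 becomes 106, 422 becomes 274 and 423 becomes 275. The limit of 105 equals the upper end of the Part 1C row for BD-Day 29, [2, 105]. The 274 differs from Part 1C's 271 because Part 2's last visit is at booster-relative day 366, not 361: (181 + 366)/2 = 273.5, against (181 + 361)/2 = 271.

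**The case against.** The case for leaving this alone is substantial, and most of it stands.

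- **The footnote mislabels nothing.** A reader might infer that a late booster puts scheduled titers under the wrong visit. It does not: Step 1 keeps the nominal label, and Day 177 is the visit at which the sample was drawn. Only the time since booster would be off.
- **The literal reading of the footnote is strained.** It puts a visit meant to follow the injection before it on most extended days, so sites may well have followed the schedule row instead. With visits timed from a Day 170 booster, the samples fall on Days 198, 350 and 535, all inside the right windows. If dose 2 was itself on Day 50, the visits shift by 21 days and a Day 170 booster is again followed at 28 days.
- **Step 2 needs a chain of events:** a boosted Part 2 participant, a missing scheduled sample, and an unscheduled antibody sample on particular days. Appendix I requires the booster-day sample before dosing, and the only non-routine blood draw it describes is at the convalescent visit. The counts above are calendar days, not probabilities.
- **Little depends on it.** The listed Part 2 endpoints use Days 29 and 57 (Section 3.4.2) and Days 1, 57, 209 and 394 (Section 3.4.3). Section 4.2.2 rules out hypothesis tests. Section 4.1.2 of the SAP for Part 1A records that booster dosing was removed.

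What the objection does not remove is the rule itself. Followed exactly, Step 2 with these rows can place a titer on the wrong side of the booster, and the same table avoids this for Part 1C.

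**Conclusion.** The window rule is wrong as written, at the lowest priority. The exposure is confined to the descriptive by-timepoint summaries of Section 6.4.6 for boosted Part 2 participants: the geometric mean and the rise over pre-dose 1, with the proportions computed from that rise. Fold-rise over the pre-booster level is planned for Part 1C only, and the adverse event periods in Section 6.1 run from the actual injection.

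A stronger reading, that a Part 2 endpoint or any test, power or alpha is touched, has no support in the documents. The number of affected samples is unknown and may be zero. The wrong-label result assumes that a scheduled sample is missing and an unscheduled one exists. The 7-day and 14-day figures assume that sites followed the footnote literally after an on-time dose 2.

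**What to change.** - **Table 3.** State the Part 2 booster immunogenicity rows in the booster-relative study day of Section 6.1. The pre-booster value is the last sample before the injection. Post-booster rows admit only samples taken after it: the 28-day row up to day 105, the 180-day row 106 to 274, the 365-day row from 275.
- **Timing flag.** Flag any sample in the 28-day row, nominal ones included, taken fewer than 28 days after the actual booster, and show the descriptive geometric mean with and without flagged samples.
- **Footnote 2 of Appendix I.** Re-time the remaining visits from the actual date of the delayed dose (second dose or booster). This is for consistency only; with booster dosing removed, it changes no future visit.

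The cost is a few table rows, one derived flag and a few words. No new data are needed, and the labelling rule and flag can be applied to samples already taken.

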## 9.10. Appendix J Schedule of Assessments (Part 2 For Participants Who Do Not Receive The Booster Dose)

Visit Number	0	1	2	3	4	5	6	7	8	-	9	-	10
Type of Visit	C	C	Virtual Call	C	C	Virtua lCall	C	Virtua lCall	C	Virtual Call	C	SFU	C
Month/Timepoint	M0		M1		M2		M3	eDiary	SC	M7	eDiary	SC	M13
Study Visit Day													
Window Allowance (Days)	-7		+3		+7		-2		+3		+7		+7
Days Since Most Recent Injection	-	0	7	28	3	7	28	35	65	-	-	180	-
Informed consent/assent form, demographics, concomitant medications, medical history													
Review of inclusion and exclusion criteria 		X											
Physical examination including vital signs, height, weight 		X		X		X		X				X	
Pregnancy test 		X		X		X		X				X	
Study injection (including 30-minute post dose observation period)			X			X		X					
Blood sample for potential biomarker analysis 				X									

Visit Number	0	1	2	3	4	5	6	7	8	-	9	-	10
Type of Visit	C	C	Virtual Call	C	C	Virtua lCall	C	Virtua lCall	C	SFU	C	SFU	C
Month/Timepoint	M0		M1		M2		M3	eDiary	SC	M7	eDiary	SC	M13
Study Visit Day													
Window Allowance													
(Days)													
Days Since Most Recent Injection	-	0	7	28	3	7	28	35	65	-	-	180	-
Blood sample for vaccine immunogenicity 	X		X		X		X		X			X	
Nasal swab sample for SARS-CoV-2 	X		X		X		X		X			X	
Surveillance for COVID-19/ Illness visit  / Unscheduled visit	X		X		X		X		X			X	
eDiary activation for recording solicited ARs (7 days) 			X				X						
Review of eDiary data 			X				X						
Follow-up safety telephone calls 												X	
Recording of unsolicited AEs	X		X		X		X		X			X	

Visit Number	0	1	2	3	4	5	6	7	8	-	9	-	10
Type of Visit	C	C	Virtual Call	C	C	Virtua lCall	C	Virtua lCall	C	SFU	C	SFU	C
Month/Timepoint	M0		M1		M2		M3	eDiary	SC	M7	eDiary	SC	M13
Study Visit Day													
Window Allowance (Days)	-7		+3		+7	-2	+3	+7	+3	+7	+3	+7	+14
Days Since Most Recent Injection	-	0	7	28	3	7	28	35	65	-	-	180	-
Recording of MAAEs and concomitant medications relevant to or for the treatment of the MAAE 		X	X	X	X	X	X	X	X	X	X	X	X
Recording of SAEs and concomitant medications relevant to or for the treatment of the SAE 		X	X	X	X	X	X	X	X	X	X	X	X
Recording of AESI		X	X	X	X	X	X	X	X	X	X	X	X
Recording of AEs leading to withdrawal		X	X	X	X	X	X	X	X	X	X	X	X
Recording of concomitant medications and nonstudy vaccinations 		X	X	X	X	X	X	X	X	X	X	X	X
Study completion													X

Abbreviations: AE = adverse event; AESI = adverse event of special interest; AR = adverse reaction; BMI = body mass index; C = clinic visit; COVID-19 = coronavirus disease 2019; D = day; eDiary = electronic diary; FDA = USA Food and Drug Administration; IRB = institutional review

board; M = month; MAAE = medically attended AE; NP = nasopharyngeal; SC = safety (telephone) call; SFU = safety follow-up; RT-PCR = reverse transcriptase polymerase chain reaction; SAE = serious adverse event; SARS-CoV-2 = Severe Acute Respiratory Syndrome coronavirus 2.

Note: In accordance with FDA Guidance on Conduct of Clinical Trials of Medical Products during COVID-19 Public Health Emergency ([DHHS 2020](#)), investigators may convert study site visits to home visits or teledmedicine visits with the approval of the Sponsor.

Note: All scheduled study visits should be completed within the respective visit windows. If the participant is not able to attend a study site visit due to the COVID-19 pandemic (self-quarantine or disruption of study site activities following business continuity plans and/or local government mandates for “stay at home” or “shelter in place”), a safety telephone call to the participant should be made in place of the study site visit. The safety telephone call should encompass all scheduled visit assessments that can be completed remotely, such as assessment for AEs and concomitant medications (eg, as defined in scheduled safety telephone calls). Home visits will be permitted for all nondosing visits, except for Screening, if a participant cannot visit the study due to the COVID-19 pandemic. Home visits must be permitted by the study site IRB and the participant via informed consent/assent and have prior approval from the Sponsor (or its designee).

1. Day 0 and Day 1 may be combined on the same day. Additionally, the Day 0 Visit may be performed over multiple visits if they occur within the 7-day Screening window. If eligible, participants will receive 50 µg mRNA-1273 28 days apart.
2. If the visit for the second dose (Day 29) is disrupted and cannot be completed at Day 29 +7 due to the COVID-19 pandemic (self-quarantine or disruption of study site activities following business continuity plans and/or local government mandates for “stay at home” or “shelter in place”), the visit window may be extended to Day 29 + 21 days. When the extended visit window is used, the remaining study visits should be rescheduled to follow the inter-visit interval from the actual date of the second dose.
3. Safety follow-up via an eDiary questionnaire will be performed every 4 weeks from Day 99 to Day 183 and again from Day 223 to Day 307.
4. Safety follow-up via a safety telephone call will be performed every 4 weeks from Day 113 to Day 197 and again from Day 237 to Day 321.
5. Review of inclusion and exclusion criteria will be conducted during Screening. However, this review may be conducted on Day 1 if Screening and Baseline procedures are conducted on the same day.
6. Physical examination: A full physical examination, including height, weight, and vital signs will be performed at Screening, Day 1, Day 29, Day 57, Day 209, and Day 394. BMI will be calculated only at Screening Visit (Day 0). Symptom-directed physical examinations may be performed at other timepoints at the discretion of the investigator. On each injection day before injection and again 7 days after injection, the arm receiving the injection should be examined and the associated lymph nodes should be evaluated. Any clinically significant finding identified during a study visit should be reported as a MAAE. Vital signs are to be measured predose and postdose on days of injection (Day 1 and Day 29). When applicable, vital signs should be measured before blood collection. Participants who are febrile (body temperature  $\geq 38.0^{\circ}\text{C}/100.4^{\circ}\text{F}$ ) before injection on Day 1 and Day 29 must have the visit rescheduled within the relevant visit window to receive the injection. Afebrile participants with minor illnesses can be enrolled at the discretion of the investigator.
7. Pregnancy test at Screening and Day 1, and before the second study injection will be a point-of-care urine test. At the discretion of the investigator, a pregnancy test either via blood or point-of-care urine test can be performed at any time.
8. Serum sample from two ~4 mL blood draws. Biomarker plasma and biomarker serum samples will be stored for potential future biomarker assessment.
9. Sample must be collected prior to dosing of injection on Day 1 and Day 29.
10. The nasal swab sample will be used to ascertain the presence of SARS-CoV-2 via RT-PCR.
11. An unscheduled visit may be prompted by reactivity issues, illness visit criteria for COVID-19, or new or ongoing AEs. If a participant meets the prespecified criteria of suspicion for COVID-19 (**Section Error! Reference source not found.**), the participants will be asked to return within 72 hours or as soon as possible to the study site for an unscheduled illness visit, to include a nasal swab sample (for RT-PCR testing) and other

clinical evaluations. If a study site visit is not possible, a home visit may be arranged to collect the NP or nasal sample and conduct clinical evaluations. If a home visit is not possible, the participant will be asked to submit a saliva sample to the study site by a Sponsor-approved method. At this illness visit, the NP or nasal swab samples will be collected to evaluate for the presence of SARS-CoV-2 infection. NP or nasal swab samples will also be tested for the presence of other respiratory pathogens. In addition, the study site may collect an additional NP or nasal sample for SARS-CoV-2 testing to be able to render appropriate medical care for the study participant as determined by local standards of care. Additionally, clinical information will be carefully collected to evaluate the severity of the clinical case.

12. Diary entries will be recorded by the participant at approximately 30 minutes after injection while at the study site with instruction provided by study staff. Study participants will continue to record entries in the eDiary each day after they leave the study site, preferably in the evening, on the day of injection and for 6 days following injection. If a solicited local or systemic AR continues beyond Day 7 after vaccination, the participant will be prompted to capture details of the solicited local or systemic AR in the eDiary until the AR resolves or the next IP injection occurs, whichever occurs first; capture of details of ARs in the eDiary should not exceed 28 days after each vaccination.
13. ARs recorded in eDiaries beyond Day 7 after vaccination should be reviewed either via telephone call or at the following study visit.
14. Trained study site personnel will call all participants to collect information relating to any AEs, MAAEs, SAEs, AEs leading to study withdrawal, information on concomitant medications associated with those events, and any nonstudy vaccinations. In addition, study personnel will collect information on known participant exposure to someone with known COVID-19 or SARS-CoV-2 infection and on participant experience of COVID-19 symptoms.
15. All concomitant medications and nonstudy vaccinations will be recorded throughout the study; all concomitant medications relevant to or for the treatment of an SAE or MAAE will be recorded from Day 1 through the final visit (Day 394).

